*** 5. Describe the primary language that will be used by those obtaining consent.**

English*

*Component A is planning and refinement (information gathering) if it is necessary to obtain consent/parental consent/youth assent in another language (e.g., Spanish) a modification will be sent to IRB in advance.

*** 6. Describe the primary language understood by the participant. If translation services (verbal and/or written) are needed, please describe that here. If written materials are necessary a Translation Certification Form is required.**

English*

*Component A is planning and refinement (information gathering) if it is necessary to conduct a FG (or one-on-one interview); in another language (e.g., Spanish) modifications will be submitted to IRB in advance.

*** 7. Will any subjects be decisionally impaired so that they do not have the capacity to give consent?**

No

*** 8. In certain cases involving non-exempt research (i.e. Expedited or Full Board), a waiver of informed consent or a waiver of an element of informed consent may be requested. Additionally, for projects including UNL students who are 17 or 18 years of age, a waiver of parental consent may be requested. Would you like to request a waiver of consent or a waiver of a consent element?**

No

9. In certain cases involving non-exempt research (i.e., Expedited or Full Board), a waiver of informed consent documentation may be requested. Electronic consent may be a typical process where consent documentation might be waived.

Note

In the state of Nebraska, electronic signature must be individually identifiable to the person signing to constitute electronic signature.

*** Will this project request to waive consent documentation (e.g. signature)?**

No

Note

Consent documentation cannot be waived when an authorization to access Protected Health Information is required under the HIPAA regulations.

Confidentiality

*** 1. The project should make adequate provisions to maintain the confidentiality of the data. Describe how confidentiality of all records will be maintained.**

Audio recordings will be uploaded to a private UNL OneDrive/Sharepoint folder. Only those associated with the project (PI, Co-I, project coordinator or research assistants/staff ON THIS IRB PROTOCOL) will have access to these. Audio recordings will be uploaded to Rev where they will be transcribed. Once transcribed, all audio-recordings will be deleted. Transcript files will be uploaded to a private UNL OneDrive/Sharepoint folder. Only those associated with the project (e.g., PI, Co-I, project coordinator or research assistant) will have access to these.

*** 2. Will participants be identifiable during data collection or in the results? (This question should be answered "yes" if data collection is completed in an in-person setting or if data will be coded throughout the research process and a link is maintained between the code and participant identifiers.)**

Yes

*** 2.a. Describe how participants will be identified during the data collection procedures and in the data.**

The Project Coordinator will maintain a list of all youth and school personnel who participate (as well as contact information-- this is necessary to arrange the Focus Groups and cognitive interviews as well as to send reminders). After participating, all youth and school personnel will also sign a "Research Participant Compensation Confirmation" form. However, none of these identifiers will be associated with the data provided by the research participants.

*** 2.b. If the data are coded, describe if a list linking names and codes will be used. The description should include the process that will be followed to keep the list secure during and after data collection and when the list will be destroyed. If the list will continue to be stored after all data collection procedures are complete and data has been verified, a justification for long-term storage must be provided.**

A list of names associated with each focus group will be maintained by the Research Team members coordinating the focus groups (to identify who shows up/who does not). However, identifying information will not be associated with any of the focus group data collected. Lists of participants will be kept in separate files from the audio-recordings or transcripts. Lists of participants will be destroyed after data collection (other than participant payment forms kept on file).

The research conducting the one-on-one interviews will also know the name of the youth they are interviewing. However, this information will not be associated with the interview data, but in a separate file for record keeping purposes only.

Data will be stored online 7 years post publication.

*** 3. Describe how long the project records and data will be kept. The description should differentiate between the length of storage time for identifiable and de-identified records, if applicable.**

Audio recordings will be kept only until they are transcribed (no more than one year). De-identified transcripts will be kept for seven years and then destroyed.

*** 4. Describe where and how records and data collected will be stored. The description should include how both electronic and/or paper/physical records and data will be stored. Specificity regarding secure UNL servers vs. external servers possibly utilizing cloud computing must be provided, if applicable.**

A list of names associated with each focus group will be maintained by the Research Team members coordinating the focus groups (to identify who shows up/who does not). However, identifying information will not be associated with any of the focus group data collected. Lists of participants will be kept in separate files from the audio-recordings or transcripts. Lists of names will be destroyed following the completion of data collection although they will be maintained in payment and consent/assent forms).

The research conducting the one-on-one interviews will also know the name of the youth they are interviewing. However, this information will not be associated with the interview data, but in a separate file for record keeping purposes only.

Lists of participants will be kept in a password protected computer by the Project Coordinator and in a private UNL onedrive folder with access limited to project personnel. Participant lists will be kept for 7 years and then destroyed.

Signed consent forms / youth assent forms will be scanned and uploaded to a private UNL Onedrive folder; once scanned the original paper copies will be shredded; parental permission forms will be kept in a private UNL Onedrive folder.

*** 5. Describe all persons or entities planning to have access to the records and/or data.**

Only project personnel will have access to the data: Project Coordinator, PI, Co-I, research assistants/staff on this IRB protocol. Rev will have access to the audio-recordings as well in order to transcribe.

*** 6. Describe how data and/or research results will be reported. The description should include whether the data will be reported individually, identifiable, or in summary (aggregate) format. This description should also consider the possibility of deductive disclosure when reporting results or describing the research in a manuscript. If applicable, describe if masking procedures or certain descriptions would or would not be used. Also, describe if the data/results will be reported at conferences, in journals, in a thesis, in a dissertation, to the funding agency, back to the project site, etc.**

All data will be reported in aggregate form only; names or participant identifying information will not be used.

Data Monitoring & Sharing

*** 7. Does the project require data safety monitoring?**

Yes

*** 7.a. Describe the provisions for monitoring the data to ensure the safety of participants. For example, in a clinical drug trial study, the data is monitored as it is collected to detect adverse side effects. If participants are having serious reactions to the study drug, then the study is adjusted to protect the participants. A second example would be in a study on teen suicide, if a teen exhibits signs of suicidal tendencies, a process is in place to notify the appropriate people immediately rather than realizing the problem at the end of the study.**

At this point in the project, the research team will be monitoring the data for safety. This will involve de-briefing with all data collectors for both the FGs and cognitive interviews; having at least 2 researchers present at each FG; contacting the PI immediately if any problems or unexpected events arise at the FG or cogn. interviews.

*** 7.b. Identify what data will be reviewed.**

Information provided at the FG and cognitive interviews.

*** 7.c. Describe how often the data will be reviewed.**

The research team will be monitoring the data provided by participants for as the data are being collected (during FG or interviews). The PI will be contacted if any problems are detected (e.g., personal disclosures; individuals showing up without proper consent/parental consent/assent; upset at the questions or emotional distress).

*** 7.d. Describe what actions would be considered during the review of the data.**

The PI will be contacted immediately. Actions will result depending on what the issue is (e.g., informing that a person was asked to leave a FG because he/she showed up without having received parental consent; pausing the cognitive interview if a break is needed, etc...). All incidents will be recorded. IRB will be notified in cases including, but not limited to: mandatory reporting required, person stopping the FG or cogn. interview because of being upset; person not allowed to participate in FG bc parental consent not obtained.

*** 8. Do you plan to share the data collected during this project through public-use files, repositories or other means outside of your approved research team and/or sites?**

No

Note

If data sharing plans change at any time, please contact your IRB coordinator to discuss the necessary steps, as applicable.

Questionnaires, Surveys, and Testing Instruments

*** Please list all questionnaires, surveys, and/or assessment instruments/measures used in the project.**

Focus group script- school personnel
Focus group script- youth
Cognitive interview- youth
Demographics (school personnel and youth)

*Please note that we will come back with a change request form with the surveys for the cognitive interviews, branding for fliers/consents, and other edits after working more with our school partners to obtain their input. We are also in the process of discussing plans for putting together adult and youth advisory boards and will let the IRB know about these as well. Just like other boards in PI [name] work, these individuals will provide guidance/input on all study protocols that are submitted to the IRB.

**The funded grant proposal is also uploaded.

Uploaded Attachments

Please submit copies of the following:

- **Funding application**
- **Institutional Approval letters**
- **Data sharing plans**
- **Recruitment flyers, ads, phone scripts, emails, etc.**
- **Informed Consent Forms, emails, and/or letters**
- **If transcriptions are required, Confidentiality Agreement that transcriptionists will sign**
- **If this is a study utilizing PHI, Release of Authorization that will be used to obtain permission from the participant for the agency/institution to release protected health information for project purposes or a letter from the agency/institution documenting agreement to provide protected health information for project purposes**
- **All Instruments/Measures used in the project**

Please upload all documents that would include the IRB approval stamp as a PDF. These documents could include recruitment materials AND informed consent/assent forms.

letter of support (2) from [name] for SMF-UNL project TA signed.pdf
[name] CDC proposal 2-1-22.pdf
Rev.com Information Security Privacy Overview.pdf
Resource Sheet - Des Moines, IA.docx
Cognitive Interview Script_Youth.docx
Demographics, School Personnel.docx
Demographics, Youth.docx
PC_Youth Recruitment Script.docx
Recruitment Flyer.docx
Research Participant Compensation Confirmation.docx
Focus Group Scripts_School Personnel (2).docx
Focus Group Scripts_Youth.docx
Reminder Script.docx
Youth_ParentPermissionReceived(PPR) Script.docx
Parental Contact and Permission Script.docx
Caregiver Consent_Cognitive Interview_11.8.22.docx
Caregiver Consent_Focus Group_11.8.22.docx
Consent_School Personnel_11.8.22.docx
Youth Assent_Cognitive Interview_11.8.22.docx
PC_School Personnel Recruitment Script_11.8.22.docx
Youth Assent_Focus Group_11.8.22_RW edits.docx
Youth Assent_Focus Group_11.8.22_RW edits-Approved.pdf
Youth Assent_Cognitive Interview_11.8.22-Approved.pdf
Caregiver Consent_Cognitive Interview_11.8.22-Approved.pdf
Consent_School Personnel_11.8.22-Approved.pdf
Caregiver Consent_Focus Group_11.8.22-Approved.pdf

ClinicalTrials.gov Data Entry Cover Sheet

Protocol ID: 22811 **Clinical Trials.gov ID:** NCT05988398

Project Title: Preventing Commercial Sexual Exploitation of Children (Project LIVE)

Principal Investigator: [name], University of Nebraska-Lincoln

Statistical Design and Power

Power Analyses

Aim 1a. N/A

Aim 1b. There is no “magic bullet” for sample size in qualitative research.¹²⁷⁻¹²⁹ The sample size proposed for focus groups is consistent with other research conducted by the PI and Co-I ([name]) that should allow for saturation (i.e., the collection of new data does not produce additional insights).¹³⁰ However, the sample size may be adjusted until data saturation is achieved.¹³⁰

Aim 1c. N/A

Aim 1d. Power analyses to support the sample size for the measurement development study (for multi-item measures) are based on prior simulation work.¹³¹ The proposed sample size of $n=878$ baseline surveys from youth will be utilized by splitting the sample in half to conduct exploratory factor analysis (EFA) and confirmatory factor analysis (CFA), each with 439 youth. A sample size of 439 youth is adequate for implementing factor analyses using structural equation modeling approaches and provides power ($> .80$) to estimate two factor models, five manifest indicators each, nonnormal data, and factor loadings = .80.

Aim 1e. Regarding qualitative data, see narrative above for Aim 1b. Also, power analyses were not conducted for descriptive data (e.g., frequencies of the number of sessions attended, extent to which sessions were delivered with fidelity). Regarding student survey data collected as part of the OPT, we will examine changes in intermediary outcomes (see Figure 1) over time given that there will likely not be a sufficient window of time to see changes in behavioral primary and secondary outcomes at the immediate post-test which will happen within a few days to a week or two following the ending of the programming. For the exploratory program impact analysis on intermediary outcomes (Figure 1), a sample size of $n=878$ (approximately .5 assignment rate to condition), will provide adequate power (.80; $\alpha=.05$) to detect a minimum effect size (MDES) $d=.20$ as determined by G-Power analysis of covariance (ANCOVA) routine.

Aim 1f. N/A

Aim 2a. Power analyses to support the sample size for the effectiveness analyses for our primary, secondary, and intermediary outcomes (see Figure 1) were conducted using G-Power 3.1. Power was set to .80 and $\alpha=.05$. Component A of the study will provide incidence rates which will be used to recalculate power prior to the implementation of Component B. For the purposes of this proposal, we calculated the MDES based on the proposed sample size. For the primary outcome of CSEC perpetration, there are no reliable incidence estimates in the literature on which to draw. With a sample size of 7,241 students enrolled, assuming conservative minimum incidence rates of CSEC perpetration of 1% to 5% (although we hypothesize it will be higher), we have power to detect an MDES difference between conditions, odds ratio (OR)=.49 to .75, respectively. Similarly, for secondary outcomes of CSEC victimization, we estimated a range of incidence rates from a conservation 5% to 50%+ based on literature discussed following for other types of victimization^{96, 132, 133} as well as rates of CSEC youth at increased risk (e.g., system involved, homeless)¹⁸⁻²⁰, which will be present in our sample based on DMPS data, we have the power to detect an MDES difference between conditions, odds ratio (OR)=.75 to .88, respectively. For secondary outcomes of TDV/SV perpetration and victimization, given past 12- months incidence rates¹³² (from nationally representative data from youth) of 63% for perpetration (of any type of TDV) and 69% for victimization (of any type of TDV), we have power to detect an MDES difference between conditions, odds ratio (OR)=.88 to .89. For sub-types of TDV (past 12-month incidence rates: physical victimization: 18%; sexual victimization: 18%; psychological victimization: 66%; physical perpetration: 12%; sexual perpetration: 12%; psychological perpetration: 62%)¹³², we have power to detect an MDES difference between conditions, odds ratio (OR)=.83 to .89, respectively. For the secondary outcome CSEC bystander action and opportunity and intermediary outcomes (i.e., knowledge, valuing of self and others, healthy relationship skills, bystander efficacy, perceptions of school social norms, prevention conversations with school personnel), the ANCOVA routine suggested power (.80) to detect a small difference between groups (MDES $d=.06$).

Aim 2b. For the mediation analyses, based on simulation literature^{134, 135}, a sample size of 7,241 provides power ($> .80$) to detect small effects ($a=.28$; $b=.14$), which are typical of mediation designs. For the moderation analyses, we used simulation-based approach to power analysis using Mplus¹³¹. We used a multiple group model, assuming categorical moderators (e.g., gender). The proposed sample size provides sufficient power ($> .80$) to detect moderation group differences in treatment effects, $b=.20$. As an alternative way to examine power for moderation of treatment effects, we examined the MDES within moderation groups. For this analysis (G-Power ANCOVA), we took a conservative approach and used the moderator that may have the largest discrepancy in group size, such as gender identity and sexual orientation. Based on population data, we estimate 2.5% will identify as a gender minority (inclusively defined, e.g., trans, non-binary, gender queer, Two Spirit)¹³⁶⁻¹³⁸, leaving a sample size of $n=181$; and 10% of the sample will identify as a sexual minority^{113, 139}, leaving a sample size of $n=724$. Simulation power analysis supports being able to detect a small condition group difference, MDES $d=.20$.

Aim 2c. N/A

Aim 2d. N/A

Aim 2f. N/A

Proposed Analyses

Aim 1a. N/A

Aim 1b. Under the leadership of Co-I [name], data will be analyzed using thematic analysis.^{90, 91} More specifically, audio files will be transcribed (using Rev, a speech to text on-line transcriptions service), de-identified by a member of the research team, and then read thoroughly to become familiar with the data. Initial codes are then created that represent the meaning and patterns evident in the data. A codebook is created simultaneously to keep track of the codes. The next step involves reading data again and applying codes to excerpts/passages that correspond to codes. Excerpts that represent the same meaning(s) receive the same code. Next, all excerpts with the same code are grouped together. The codes are then grouped into potential themes; with some themes having sub-themes. Themes are then reviewed and revised, ensuring that each theme has enough data to support it as a distinct concept. Themes are then arranged in narrative communicating results of analysis. Although school personnel data will be analyzed separately from student data, we will examine similarities and differences in themes across these populations. We will also examine variations in themes across subpopulations of students as well as subpopulations of school personnel. Themes will be shared with the RAB and their input on how to use this data to inform programming and research will be solicited.

Aim 1c. N/A

Aim 1d. Rigorous psychometric evidence for the newly developed multi-item measures will be evaluated using multiple indices (as most applicable to each measure) as guided by the American Educational Research Association standards⁹². First, using data from the baseline (pretest), we will randomly assign students to either Phase 1 (EFA; $n=435$) or Phase 2 (CFA; $n=435$) to determine evidence of internal measurement structure. In Phase 1, we will examine the factor structure by conducting EFA using the common factor model and full information maximum likelihood (FIML) estimation with oblique rotation within a structural equation modeling (SEM) framework¹⁴⁰ in Mplus¹⁴¹. This rigorous method retains all cases with the assumption that any missing responses are missing at random (MAR) to maintain power and improve estimation under conditions of missing data¹⁴². We will employ parallel analysis to determine the appropriate number of factors¹⁴⁰ (and then evaluate the fit of the model within SEM)¹⁴⁰. After conducting the EFA, we will then replicate the measurement structure in a new sample of students using CFA within SEM with FIML. We will also examine internal consistency estimates of reliability of our measures. Next, we will examine evidence of convergent associations between the newly developed measures with existing, psychometrically sound measures (see Table 3). Structural regression models will be estimated including a latent and manifest measurement model and regression paths to determine associations between the newly developed multi-item and single-item measures and existing measures to determine if associations are in the theoretically derived hypothesized

direction. Model fit will be determined using multiple indices, including chi-square statistic, root mean square error of approximation (RMSEA ≤ 0.08), the comparative fit index (CFI ≥ 0.90), and the standardized root mean square residual (SRMR ≤ 0.10)¹⁴³.

Aim 1e. Regarding qualitative data, see narrative above for Aim 1b. Descriptive analyses will be used to gauge things such as the average number of sessions attended, the extent to which sessions were delivered with fidelity, etc. Regarding pre- to post- changes in intermediary variables, we will use analysis of covariance, including the baseline measurement of the outcome as a covariate, the condition as the independent variable, and the post-test measure of the outcome as the dependent variable. The analysis will examine differences between conditions to determine preliminary program impact and effect sizes. Maximum likelihood estimation will be used to account for missing data in the analyses. Classroom will be used as a cluster variable to adjust the standard errors for nesting.

Aim 1f. N/A

Aim 2a and 2b.

Preliminary Analyses.

We will guard against differential attrition across experimental conditions. We will track and examine if attrition rates differ for the experimental groups. We expect similar rates of attrition across experimental groups. Furthermore, we will use data from all enrolled cases, who all have baseline data based on our design in our analyses to limit the bias introduced by missing data. Missing data assumed to be at least MAR will be dealt with as a function of the data analytic process through maximum likelihood estimation (ML), which makes use of all available data and does not require deletion of incomplete cases.

Outcome Analyses (Aim 2a).

We will test the hypotheses related to examining effectiveness of participation in the RTS in leading to reductions in CSEC perpetration (primary outcome), as well as reductions in CSEC victimization and TDV and SV victimization and perpetration and increases in bystander intervention in CSEC situations (secondary outcomes). To improve the rigor of analyses for Aim 2a, we will use propensity-score analysis to reduce the impact of selection bias, and latent constructs, when possible, to reduce measurement error, reduce paths and variables, and increase statistical power (MacCallum et al., 1996). This approach produces rigorous estimates of causal effects within the context of quasi-experimental designs when random assignment is not possible by controlling confounders, including selection effects¹⁴⁴. This approach will use four analytic steps: (1) estimate propensity scores in a separate analysis, (2) use the propensity scores to adjust for confounding, (3) assess balance, and (4) estimate the propensity score-adjusted treatment effects (Lanza et al., 2013). In step 1, to estimate the propensity score, we will consider all pertinent confounders and covariates (see Measurement Table 3). This step will use logistic regression of condition on the potential confounders to obtain each student's propensity score. All measured confounders that are predictive of selection into the experimental conditions and the outcomes will be included in the propensity model. Standardized mean differences in covariate values across treatment and comparison conditions will be used to determine the final set of confounders to include in estimating the propensity score. In step 2, an initial treatment effect model is estimated that adjusts for confounding using the propensity score. We will use inverse probability weighting (IPTW) to adjust for confounding. The standardized mean differences between experimental groups are computed on the weighted sample included the IPTW-adjusted propensity score (Step 2). If IPTW does not provide optimal balance, then other methods will be considered (e.g., matching). Then Step 3 is used to determine balance on the potential confounders included in the propensity score across the experimental groups. The goal is to determine whether there are any differences remaining on the confounders between experimental groups (balance = standardized mean differences $< |0.2|$ after adjustment). Confounders will be adjusted and the propensity score model (Step 1) will be re-estimated until balance is reached. Once balance is determined, the outcome analysis will be conducted in Step 4 via SEM. The experimental effect of interest will be the Average Treatment Effect (ATE), which is the population-level average effect of condition on the primary and secondary outcomes as detailed in the logic model. The effects of interest quantified are differences between experimental conditions at post-test and follow-up on outcomes (for continuous measures), the propensity score as a covariate. These effects indicate whether the outcomes in the experimental condition differ significantly from those in the comparison condition. At post-test and follow-up, we expect the difference between the experimental conditions to be significantly greater than zero, reflecting better outcomes for those in the RTS program as compared to those in the wait-list condition, after adjusting for the

propensity score. For categorical variables, logistic regression will be used to examine differences in prevalence by condition. The experimental condition is the independent variable in these models. Multilevel modeling is not possible given the small number of schools; thus, school will be included as a covariate. Classroom will be used as a cluster variable to adjust the standard errors for nesting. Models for Step 4 will be evaluated for overall model fit via χ^2 statistic, RMSEA :s .08, SRMR :s .10, and CFI \geq .90. We will evaluate our hypotheses across several indicators, including significance (p), confidence intervals, and the standardized difference between groups (d), as well as the directionality of included path coefficients, and odds ratios.

Mediation and Moderation Analyses (Aim 2b).

We will assess mediators (e.g., perceptions of norms intolerant of CSEC) and demographic moderators (e.g., gender) of program effectiveness, including the propensity score and school as covariates in all models. To test for mediation, we used the product of coefficients method using bias-corrected bootstrapping with 1000 resamples to calculate the confidence intervals¹⁴⁵ (MacKinnon, 2012). For our moderators (e.g., age, gender, racial groups, sexual orientation), we will estimate structural equation multiple group models, first allowing estimation of the path coefficients to vary freely across groups, and then constraining paths to be equal when a structural path coefficient of interest was significant for one group and not the other group. We will conduct model comparisons using the chi-square (χ^2) difference test (i.e., χ^2 , $p < .05$ indicating moderation).

Aim 2c. Descriptive statistics will be used to examine the extent to which sessions were delivered with fidelity. Process observations will be analyzed using thematic analysis as described above for Aim 1b.

Aim 2d. Descriptive statistics will be used to examine the frequency of responses to close-ended questions (e.g., To what extend did you like the session today?). Open-ended questions will be analyzed using thematic analysis as described above for Aim 1b.

Aim 2e. Interview data will be analyzed using thematic analysis as described above for Aim 1b.

Aim 2f. The purpose of this aim is to determine costs associated with the program implementation to inform future economic evaluation of the RTS. The process for documenting costs are described in Section C.18.

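### Aim 2a power: the SAP does not say whether tests are one- or two-sided; its detectable odds ratios fit one-sided .05, and two-sided power on the primary outcome is about 70%, not 80%

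*SAP*

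**What the plan says.** The Aim 2a paragraph under Power Analyses in the SAP fixes the error rates in one sentence: "Power was set to .80 and $\alpha=.05". The sample size is taken as given: "we calculated the MDES based on the proposed sample size". For the primary outcome, CSEC perpetration at 1% and 5% incidence among 7,241 enrolled students, it concludes: "we have power to detect an MDES difference between conditions, odds ratio (OR)=.49 to .75, respectively".

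For any TDV (63% perpetration, 69% victimization) it says "we have power to detect an MDES difference between conditions, odds ratio (OR)=.88 to .89". For TDV sub-types, with rates from 12% to 66%, it gives "odds ratio (OR)=.83 to .89, respectively".

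The Outcome Analyses (Aim 2a) section is the other place where sidedness could be declared. It says "These effects indicate whether the outcomes in the experimental condition differ significantly from those in the comparison condition" and then, of post-test and follow-up, "we expect the difference between the experimental conditions to be significantly greater than zero". Both sentences belong to the description of continuous measures. For binary outcomes it says "For categorical variables, logistic regression will be used to examine differences in prevalence by condition", with p-values and confidence intervals among the criteria. Neither sidedness nor a confidence level is given.

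**The concern.** An unqualified alpha of .05, with an analysis that looks for differences in prevalence, is ordinarily read as a two-sided test. On that reading the printed odds ratios sit too close to 1 for 7,241 students at 80% power. A reader would then believe the risk of missing the stated primary effect is 20% when it is about 30%.

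Two later steps depend on the answer. The SAP promises to recalculate power with Component A incidence rates before Component B starts, and that calculation could carry the same unstated setting forward. A null result on CSEC perpetration would also be read against a power that may not have been delivered. If sidedness stays open until results are seen, the threshold for p can be chosen then.

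**Working it through.** **Inputs.** From the SAP's Aim 2a power paragraph: N = 7,241, power .80, alpha .05, and the incidence rates and odds ratios above. Assumed: 1:1 allocation (n = 7,241/2 = 3,620.5 per arm; Aim 2a gives no ratio, Aim 1e gives about .5), incidence taken as the comparison-arm rate p1, no clustering and no attrition.

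**Formulas.** The rate under the program is p2 = p1·OR / (1 − p1 + p1·OR). With p̄ = (p1 + p2)/2:

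- SE0 = √[2p̄(1 − p̄)/n]
- SE1 = √{[p1(1 − p1) + p2(1 − p2)]/n}
- power = Φ[(p1 − p2 − z·SE0)/SE1], with z = 1.645 one-sided or 1.960 two-sided

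**Primary outcome, 5% and OR .75.** p2 = .0375/.9875 = .03797; difference .01203; SE0 = .00482; SE1 = .00482.

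- One-sided: (.01203 − 1.645 × .00482)/.00482 ≈ .85, power 80.2%.
- Two-sided: (.01203 − 1.960 × .00482)/.00482 ≈ .54, power 70.4%.

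**Primary outcome, 1% and OR .49.** p2 = .0049/.9949 = .00493; difference .00508; SE0 and SE1 about .00202.

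- One-sided: argument .864, power 80.6%.
- Two-sided: argument .549, power 70.9%.

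A one-sided test therefore reproduces the SAP's primary figures.

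**All pairs.** Solving the same formula for the odds ratio at 80% power, and evaluating two-sided power at the printed odds ratio:

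| Incidence | Printed OR | One-sided .05 | Two-sided .05 | Two-sided power at printed OR |
|---|---|---|---|---|
| 1% | .49 | .494 | .440 | 70.9% |
| 5% | .75 | .751 | .722 | 70.4% |
| 12% | .83 | .830 | .810 | 70.0% |
| 62% | .89 | .887 | .874 | 67.8% |
| 63% | .89 | .887 | .873 | 67.4% |
| 69% | .88 | .883 | .869 | 72.1% |

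The one-sided column rounds to the printed figure in every row; the two-sided column does so in none. Because the any-TDV range carries no respective ordering, .89 is paired here with 63% and .88 with 69%, as the one-sided solution gives.

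**A check that does not depend on the pairing.** Across all incidences, the two-sided detectable odds ratio closest to 1 is about .877, near 51%. A printed .89 cannot come from a two-sided .05 test with these inputs.

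**Other methods.** The Wald log-odds-ratio formula agrees to about .001, except at 1%, where it gives .485 one-sided and .426 two-sided and power at .49 is 69.1% two-sided. Unpooled, arcsine, continuity-corrected and inverted-odds-ratio versions do not rescue a two-sided reading of the set. Taking the rate as the overall incidence gives two-sided values of .503, .738 and .816 at 1%, 5% and 12%; taking it as the treated-arm rate gives .561, .753 and .823. Neither matches. Varying allocation from 30:70 to 70:30, the best two-sided power is 71.2% for the primary pairs and 72.1% for any pair.

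**Students needed for 80% two-sided power at the printed primary odds ratios** (pooled to Wald):

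- 1%, OR .49: 9,027 to 9,410, or 1.25 to 1.30 times 7,241
- 5%, OR .75: 9,128 to 9,185, or 1.26 to 1.27 times 7,241

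**The case against.** The strongest reply is that nothing has been miscalculated. The printed values are right for a one-sided .05 test, the hypotheses are directional (reductions in perpetration and victimization, increases in bystander action), and the SAP never promises a two-sided test. This stands in part: the shortfall is conditional. But a directional hypothesis does not declare a one-sided test, and no such declaration appears in either section.

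Four narrower points also deserve weight:

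- **CSEC victimization.** The SAP prints .88 at 50%+. At exactly 50% that fits two-sided (.877) and not one-sided (.890). One-sided gives .88 at about 66-75%, which 50%+ also covers. This figure settles nothing, and the claim about the set leaves it out.
- **Pairing of the TDV figures.** In printed order (63% with .88, 69% with .89), two-sided power is 75% and 64%, and at 66% with .89 it is 66%. The range moves, but all remain below 80%. The primary pairs are stated respectively and are unaffected.
- **Rounding.** At 62-63% with .89, even one-sided power is about 78%, so about 2 points of the shortfall there come from two-decimal rounding. The primary figures are clean.
- **Consequence.** The sample size was not derived from these odds ratios, the primary incidence rates are placeholders that the sponsor expects to be exceeded, and a recalculation is already planned. This limits the harm, but the recalculation needs the sidedness fixed first.

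**Conclusion.** The concern holds. Sidedness is not stated, and the primary-outcome and TDV odds ratios are those of a one-sided .05 test (numerically the same as two-sided .10). Read as two-sided .05, the section overstates power on the primary outcome by about 10 points: 69-71% at 1% incidence and 70% at 5%, against the stated 80%. For the TDV pairs in the table it is 67-72%.

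The figures rest on 1:1 allocation, no clustering and no attrition. The student numbers show the size of the gap and are not enrollment targets, since the planned analysis also uses weighting, a school covariate and classroom-clustered standard errors. The design is not invalidated; this is a correction to make before Component B.

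**What to change.** State in both the Aim 2a power paragraph and the Aim 2a outcome-analysis section whether the tests are one- or two-sided, and give the matching confidence level.

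- **If two-sided .05:** restate the detectable odds ratios as about .44 (1%), .72 (5%), .81 (12%), .88 (50%) and .87 (62-69%).
- **If one-sided .05:** keep the primary and TDV odds ratios, declare the test in both places, and give the exact incidence behind the .88 for CSEC victimization, because .88 does not fit one-sided at 50%.

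State the allocation ratio used, and carry the same sidedness into the recalculation before Component B. The cost is SAP wording and, if two-sided, slightly less favorable detectable effects.
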